7.2 Safety Assessments

7.2.1 Laboratory Assessments

- See [Section 10.6 Appendix 6: Clinical Laboratory Assessments] for the list of clinical laboratory tests to be performed and refer to the schedules of assessments [[Table 1](#) through [Table 3](#)] for timing and frequency.
- The investigator must review the laboratory report, document this review, and record any clinically significant changes occurring during the study as an AE. The laboratory reports must be filed with the source documents.
- Clinical significance of out-of-range laboratory findings is to be determined and documented by the investigator or subinvestigator who is a qualified physician. Abnormal laboratory findings associated with the underlying disease are not considered clinically significant unless judged by the investigator to be more severe than expected for the participant's condition.
- Laboratory assessments must be submitted for centralized data entry.

7.2.2 Vital Signs

- Oral temperature, pulse rate, respiratory rate, and blood pressure will be assessed as specified in the schedules of assessments [[Table 1](#) through [Table 3](#)].
- Blood pressure and pulse measurements will be assessed with a completely automated device. Manual techniques will be used only if an automated device is not available.
- Blood pressure and pulse measurements should be preceded by at least 5 min of rest for the participant in a quiet setting without distractions (e.g., television, cell phones).
- Vital signs will be measured in a semi-supine position after 5 min of rest and will include temperature, systolic and diastolic blood pressure and pulse.

7.2.3 Physical Examination

The investigator or designee (a physician or licensed practitioner) will perform standard, full physical examinations as specified in the schedules of assessments [[Table 1](#) through [Table 3](#)]. Height and body weight will be measured at the screening visit, and the body weight measurement will be repeated at day 1 of each cycle. If height cannot be measured at the screening visit, it can be collected at any time during the course of the study but should be recorded for the screening visit.

7.2.4 Electrocardiogram

12-lead ECGs will be recorded in triplicate (at least 2 min apart per time point) and transmitted electronically for central reading. On IP administration days, ECGs will be obtained:

- At C1D1 and any visit when pembrolizumab and ASP0739 are administered together, ECGs are obtained predose (-1 h from start of pembrolizumab infusion) and 1 to 2 h post dose of ASP0739.
- ASP0739 dosing only: ECGs are obtained predose (-1 h from start of ASP0739 infusion) and 1 to 2 h post dose of ASP0739.
- Pembrolizumab dosing only: ECGs are obtained predose (-1 h from start of pembrolizumab infusion) and 1 to 2 h post dose of pembrolizumab.

ECGs will be recorded after the participant has been in a resting, supine position for at least 5 min. Further details of the procedure will be separately specified in the procedural manual.

7.2.5 Imaging

Radiographic disease assessment is to be performed at screening and throughout the study every 56 ± 7 days. The same technique (CT/MRI) used at screening should be utilized throughout the study. Imaging should include chest, abdomen and pelvis, as well as any other anatomical region appropriate for the participant's disease. Scans performed prior to informed consent as SOC are acceptable as screening scans, if done within 28 days prior to C1D1.

7.2.6 ECOG Performance Status

The ECOG Scale [Oken et al, 1982] will be used to assess performance status [[Table 10](#)] at time points outlined in the schedules of assessments [[Table 1](#) through [Table 3](#)].

Table 10 ECOG Performance Status

Grade	Description
0	Fully active, able to carry on all predisease performance without restriction.
1	Restricted in physically strenuous activity, but ambulatory and able to carry out work of a light or sedentary nature, e.g., light house work, office work.
2	Ambulatory and capable of all self-care, but unable to carry out any work activities. Up and about more than 50% of waking hours.
3	Capable of only limited self-care, confined to bed or chair more than 50% of waking hours.
4	Completely disabled. Cannot carry on any self-care. Totally confined to bed or chair.
5	Dead.

ECOG: Eastern Cooperative Oncology Group

7.2.7 Order of Assessments

The following order should be followed when more than one assessment is required at a time point with blood sampling for pharmacokinetics/metabolic profiling being collected nearest to the scheduled time point:

- ECG
- Vital signs
- Blood collection

7.3 Adverse Events and Other Safety Aspects

The definitions of an AE or SAE can be found in [Sections [10.3.1](#) and [10.3.2](#)], respectively. AEs will be reported by the participant (or, when appropriate, by a caregiver, surrogate, or the participant's legally authorized representative).

The investigator and any qualified designees are responsible for detecting, documenting and recording events that meet the definition of an AE or SAE and remain responsible for following up AEs that are serious, considered related to the study IP and other procedures, or that caused the participant to discontinue the IP and other procedures and/or study [see Section [10.3](#) Appendix 3: Adverse Events: Definitions and Procedures for Recording, Evaluating, Follow-up and Reporting].

The method of recording, evaluating, and assessing causality of AE and SAE and the procedures for completing and transmitting SAE reports are provided in [Section [10.3](#) Appendix 3: Adverse Events: Definitions and Procedures for Recording, Evaluating, Follow-up and Reporting].

7.3.1 Time Period and Frequency for Collecting Adverse Event and Serious Adverse Event Information

All SAEs will be collected from the signing of the ICF until the follow-up visit at the time points specified in the schedule of assessments [[Table 1](#) through [Table 3](#)] and reported on the eCRF.

All AEs will be collected from the signing of the ICF until the follow-up visit at the time points specified in the schedule of assessments [[Table 1](#) through [Table 3](#)] and reported on the eCRF.

If the NCI-CTCAE grade/grade of an SAE/AE changes, the event should be relisted on the eCRF with the new NCI-CTCAE grade/grade and new onset date.

If the NCI-CTCAE grade/grade of an SAE/AE decreases, the SAE/AE should be relisted on the eCRF with the new NCI-CTCAE grade/grade and new onset date. The exception is ongoing pre-dose events that continue post-dose and improve post-dose. Such events should not be re-listed.

If the NCI-CTCAE grade/grade of an SAE reduces, the details of the AE should be provided on the SAE worksheet for the medical assessor to be able to assess the course of the event.

All SAEs will be recorded and reported to the sponsor or designee immediately and under no circumstance should this exceed 24 hours, as indicated in [Section 10.3 Appendix 3: Adverse Events: Definitions and Procedures for Recording, Evaluating, Follow-up and Reporting]. The investigator will submit any updated SAE data to the sponsor within 24 hours of it being available.

Investigators are not obligated to actively seek AE or SAE after conclusion of the study participation. However, if the investigator learns of any SAE, including a death, at any time after a participant has been discharged from the study, and he/she considers the event to be reasonably related to the study IP or study participation, the investigator must promptly notify the sponsor.

7.3.2 Method of Detecting Adverse Events and Serious Adverse Events

Care will be taken not to introduce bias when detecting AEs and/or SAEs. Open-ended and non-leading verbal questioning of the participant is the preferred method to inquire about AE occurrences.

7.3.3 Follow-up of Adverse Events and Serious Adverse Events

After the initial AE/SAE report, the investigator is required to proactively follow each participant at subsequent visits/contacts. All SAEs (and AEs of special interest [as defined in Section 10.3.7 Reporting Procedures for Special Situations]) will be followed until resolution, stabilization, the event is otherwise explained, or the participant is lost to follow-up (as defined in [Section 8.3]). Further information on follow-up procedures is provided in [Section 10.3 Appendix 3: Adverse Events: Definitions and Procedures for Recording, Evaluating, Follow-up and Reporting].

If after the protocol-defined AE collection period (see [Section 7.3.1 Time Period for Collecting Adverse Event and Serious Adverse Event Information]), an AE progresses to an SAE, or the investigator learns of any (S)AE (SAE or AE) including death, where he/she considers there is reasonable possibility it is related to the IP or study participation, the investigator must promptly notify the sponsor.

7.3.4 Regulatory Reporting Requirements for Serious Adverse Events

- Prompt notification by the investigator to the sponsor of an SAE is essential so that legal obligations and ethical responsibilities towards the safety of participants and the safety of a study IP under clinical investigation are met.
- The sponsor has a legal responsibility to notify both the local regulatory authority and other regulatory agencies about the safety of a study IP under clinical investigation. The sponsor will comply with country-specific regulatory requirements relating to safety reporting to the regulatory authority, IRB/IEC and investigators.
- Investigator safety reports must be prepared for suspected unexpected serious adverse reactions (SUSAR) according to local regulatory requirements and sponsor policy and forwarded to investigators as necessary.
- An investigator who receives an investigator safety report describing an SAE or other specific safety information (e.g., summary or listing of SAEs) from the sponsor will

review and then file it along with the Investigator's Brochure and will notify the IRB/IEC, if appropriate according to local requirements.

7.3.5 Disease-related Events and/or Disease-related Outcomes Not Qualifying as Adverse Events or Serious Adverse Events

Under this protocol, the following event(s) will not be considered as an (S)AE:

- Disease progression: events including defined study endpoints that are clearly consistent with the expected pattern of progression of the underlying disease are not to be recorded as (S)AEs. These data will be captured as efficacy assessment data as outlined in [Section 7.1 Efficacy Assessments]. If there is any uncertainty as to whether an event is due to anticipated disease progression and/or if there is evidence suggesting a causal relationship between the IP and the event, it should be reported as an (S)AE. All deaths up to 30 days after the final administration of IP must be reported as an SAE, even if attributed to disease progression.
- Pre-planned and elective hospital/clinical procedures/interventions or procedures for diagnostic, therapeutic, or surgical procedures for a pre-existing condition that did not worsen during the course of the study. For example, admission for treatment of a pre-existing condition not associated with the development of a new AE or with a worsening of the preexisting condition such as transfusion for preexisting anemia, leukopenia or thrombocytopenia will not be reported as an SAE. These procedures are collected per the eCRF's completion guidelines.

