9.4.3.1 Adverse Events

AEs will be coded using MedDRA and graded using NCI-CTCAE v5.0.

A treatment-emergent adverse event (TEAE) is defined as an AE observed after starting administration of the IP until 30 days after the final administration of IP. An IP-related TEAE is defined as any TEAE with a causal relationship assessed as “yes” by the investigator.

The number and percentage of participants with TEAEs, drug-related TEAEs, serious TEAEs, drug-related serious TEASs, TEAEs leading to withdrawal of treatment and drug-related TEAEs leading to withdrawal of treatment will be summarized by SOC, preferred term and treatment group. The number and percentage of TEAEs by severity will also be summarized. The worst severity will be summarized if the same AE is recorded more than once for a participant.

AE data will be listed.

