10.3.1 Definition of Adverse Events

AE Definition:

An AE is any untoward medical occurrence in a participant or clinical study participant, temporally associated with the use of study IP, whether or not considered related to the study IP.

“Adverse event” means any untoward medical occurrence associated with the use of a drug in humans, whether or not considered drug related.

NOTE: An AE can therefore be any unfavorable and unintended sign (including an abnormal laboratory finding), symptom, or disease (new or exacerbated) temporally associated with the use of study IP. This includes events related to the comparator and events related to the (study) procedures.

Events Meeting the AE Definition

- Any abnormal laboratory test results (hematology, clinical chemistry, or urinalysis) or other safety assessments (e.g., ECG, radiological scans, vital signs measurements), including those that worsen from baseline, considered clinically significant in the medical and scientific judgment of the investigator (i.e., not related to progression of underlying disease).
- Exacerbation of a chronic or intermittent pre-existing condition including either an increase in frequency and/or intensity of the condition.
- New conditions detected or diagnosed after study IP administration even though it may have been present before the start of the study.

Events NOT Meeting the AE Definition

- Any clinically significant abnormal laboratory findings or other abnormal safety assessments, which are associated with the underlying disease, unless judged by the investigator to be more severe than expected for the participant’s condition.
- The disease/disorder being studied or expected progression, signs, or symptoms of the disease/disorder being studied, unless more severe than expected for the participant’s condition.
- Medical or surgical procedure (e.g., endoscopy, appendectomy): the condition that leads to the procedure is the AE.
- Situations in which an untoward medical occurrence did not occur (social and/or convenience admission to a hospital).
- Anticipated day-to-day fluctuations of pre-existing disease(s) or condition(s) present or detected at the start of the study that do not worsen.

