If an event is not an AE per definition in [Section 10.3.1], then it cannot be an SAE even if serious conditions are met (e.g., hospitalization for signs/symptoms of the disease under study, death due to progression of disease).

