### **6.5.2 Adverse Events**

For the purpose of safety assessments in this study, events recorded during the pre-investigational period will be classified as Baseline Signs and Symptoms. All AEs recorded on treatment including within 30 days from the last study treatment and SAEs on treatment including within 90 days of the last study treatment will be summarized.

Summaries and listings of SAEs and Serious TEAEs include SAEs upgraded by the sponsor based on review of the Sponsor's list of Always Serious terms if any upgrade was done.

The coding dictionary for this study will be Medical Dictionary for Regulatory Activities (MedDRA). It will be used to summarize AEs by SOC and PT. AEs will be graded using National Cancer Institute's Common Terminology Criteria for AEs (NCI-CTCAE).

An overview table will include the following details by dose level, phase, and overall:

- Number and percentage of participants with TEAEs
- Number and percentage of participants with IP-related TEAEs
- Number and percentage of participants with TEAE leading to death
- Number and percentage of participants with IP-related TEAE leading to death
- Number and percentage of participants with serious TEAEs and Astellas upgraded serious TEAE
- Number and percentage of participants with serious IP-related TEAEs and Astellas upgraded serious IP-related TEAE
- Number and percentage of participants with TEAEs leading to permanent discontinuation of study IP
- Number and percentage of participants with IP-related TEAEs leading to permanent discontinuation of study IP
- Number and percentage of deaths

The number and percentage of participants with TEAEs, as classified by SOC and PT will be summarized by dose level, phase, and overall. Summaries will be provided for:

- DLTs within the DLT observation period
- All DLTs
- TEAEs
- IP-related TEAEs
- Serious TEAEs and Astellas upgraded serious TEAE
- IP-related serious TEAEs and IP-related Astellas upgraded serious TEAE
- TEAEs leading to permanent discontinuation of study IP
- IP-related TEAEs leading to permanent discontinuation of study IP
- TEAEs excluding serious adverse events that equal to or exceed a threshold of 10% in any dose level
- Common TEAEs that equal to or exceed a threshold of 10% in any dose level
- TEAEs leading to death
- IP-related TEAE leading to death
- CTCAE Grade 3 or higher TEAEs
- IP-related CTCAE Grade 3 or higher TEAEs

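### Protocol 7.3.5 and 10.3.2 disagree on whether a progression death within 30 days of the last dose is an SAE, so serious and fatal TEAE counts depend on which section a site follows

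*Protocol*

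**What the plan says.** Protocol 7.3.5 opens with an exclusion for progression events that are "clearly consistent with the expected pattern of progression of the underlying disease are not to be recorded as (S)AEs". Where there is doubt about progression, or evidence of a causal link to IP, it requires (S)AE reporting. It ends with a separate rule for deaths: "All deaths up to 30 days after the final administration of IP must be reported as an SAE, even if attributed to disease progression".

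The definitions are in Appendix 3, and Protocol 7.3 sends sites there for them. Section 10.3.1 lists among the events that are not AEs "The disease/disorder being studied or expected progression, signs, or symptoms of the disease/disorder being studied", except where these are worse than would be expected for that participant. Section 10.3.2 then says of an event outside the AE definition: "then it cannot be an SAE even if serious conditions are met". One of its two examples is "death due to progression of disease". Neither section mentions the 30-day rule or points to 7.3.5.

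Protocol 9.4.3.1 defines a TEAE as "an AE observed after starting administration of the IP until 30 days after the final administration of IP", and SAP 5.2.3 uses the same window. The overview table in SAP 6.5.2 includes "Number and percentage of participants with TEAE leading to death", together with serious TEAEs, the IP-related versions of both, and a separate row for all deaths. Grade 3 or higher TEAEs are summarized by system organ class and preferred term.

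**The concern.** Both passages are current, operative text, and they answer the same question differently. A site that works from 7.3.5 reports the death within 24 hours. A site that follows the pointer in 7.3 to Appendix 3 finds progression death named as something that is not an SAE, and could reasonably send nothing.

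The 30-day limit in 7.3.5 is also the end of the TEAE window. The deaths in dispute are therefore exactly those that would enter the treatment-emergent tables. Safety, including SAEs, is a primary endpoint, and the cohorts are small enough for one inconsistently handled death to be visible in a percentage.

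**Working it through.** The plan gives no figure to reproduce. The check is to follow one case through both sets of text: a death from clearly expected progression, 20 days after the last dose, with no suspicion of a link to IP.

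| Question | Under 7.3.5 | Under 10.3.1 and 10.3.2 |
|---|---|---|
| Is it reported as an SAE? | Yes, mandatory | No, named as an example |
| Sent to the sponsor within 24 hours (7.3.1, 10.3.6)? | Yes | No |
| Entered on the eCRF as an SAE (10.3.6)? | Yes | No |
| Inside the TEAE window (9.4.3.1, SAP 5.2.3)? | Yes | Not an AE, so not applicable |
| In the serious, fatal and Grade 3 or higher TEAE tables (SAP 6.5.2)? | Yes | No |
| In the all-deaths row and in OS? | Yes | Yes |

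**Scope.** The conflict is narrow.
- Doubtful or possibly IP-related deaths are reportable under 7.3.5.
- Progression worse than expected is not excluded by 10.3.1.
- Beyond 30 days after the last dose, the general exclusion in 7.3.5 and the text of 10.3.2 agree.

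**Does the SAP settle it?** No. The sponsor upgrade in SAP 6.5.2 works from a list of terms that are always serious. It can change the seriousness of a recorded AE, but it cannot decide whether an unrecorded death is an AE. The SAP has no other rule for progression deaths in these tables.

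**Size.** One such death in a participant with no other serious TEAE adds one participant to the numerator, so the shift is 1/n.
- n = 4 (participants treated as of 06 May 2022, Protocol 2.3.1.1): 1/4 = 25.0 percentage points.
- n = 12 (approximate planned phase 1 size, Protocol 9.2): 1/12 = 8.3 percentage points.

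The shift in the Grade 3 or higher summary is the same if the participant has no other TEAE of that grade. SAP 6.5.2 also reports by dose level, where n is smaller and the shift larger.

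**Decision rules.** A DLT must be considered related to IP (Protocol 4.1). The Bayesian monitoring rule uses DLTs and drug-related TEAEs leading to death (Protocol 9.5). A progression death judged unrelated enters neither. One narrow route remains: SAP 5.2.3 counts a missing causality assessment as IP-related. Protocol 10.3.3 requires a causality assessment before the first SAE transmission, so this should be rare.

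**The case against.** The strongest reply is that the specific rule governs the general one. Section 7.3.5 states the exclusion and then, in the same bullet, makes an express and mandatory exception for this kind of death. Section 10.3.2 is a general definition. That is a sensible reading and probably the intended one. But the protocol does not say so, 10.3.2 names progression death without qualification, and 7.3 tells sites that Appendix 3 holds the definitions. The reply makes the intention likely; it does not remove the conflict.

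It can also be said that such deaths may be few, since inclusion criterion 9 requires a life expectancy of at least 12 weeks. That applies at screening, and treatment can run for six 28-day cycles (6 x 28 = 168 days, or 24 weeks), so it does not exclude them. It is true that the documents give no count.

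A reader might draw four stronger conclusions that the documents do not support.
- *The SAP cannot separate deaths by cause.* It reports fatal TEAEs, IP-related fatal TEAEs and all deaths separately, tabulates fatal TEAEs by coded term, and lists AE data. A recorded progression death would be identifiable. What is missing is a rule on whether it is counted.
- *Enrollment interruption could be missed.* That trigger is a death unrelated to progression within 30 days of dosing. It turns on attribution, not on SAE status.
- *Safety comparisons between cohorts or with other trials would be invalid.* The safety analyses are descriptive and no such formal comparison is planned.
- *A planned phase 2 cohort of 43 would carry a predictable number of affected deaths.* No rate is given, and SAP Section 1 records early termination and only part of the planned analysis.

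**Conclusion.** The conflict is real and should be corrected. For deaths from clearly expected progression up to 30 days after the last dose, one section requires an SAE report and another says the event cannot be an SAE. The serious, fatal and Grade 3 or higher TEAE counts follow whichever section the site used.

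The effect per death is 1/n, subject to the condition on other serious TEAEs shown above. The total effect is unknown and would be zero if no such death occurred. All-cause deaths and OS do not change. DLTs, IP-related fatal TEAEs and the Bayesian safety rule are largely untouched. This is inconsistent reporting text that carries through to descriptive tables; it does not undermine the trial's decision rules.

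**What to change.** 1. **Protocol 10.3.1/10.3.2.** Add one sentence saying that, as an exception to the exclusion of progression events, any death up to 30 days after the final IP is reported as an SAE under 7.3.5 whatever its attributed cause.
2. **SAP 6.5.2.** State that deaths reported under that rule are counted in the serious and fatal TEAE tables, and identify those attributed to progression, for example by a footnote or a flag in the listing. A second full set of tables is not needed.

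With the study ended early, the protocol sentence may affect few or no further reports. The SAP statement is still useful, because SAP Section 1 says the final plan is to be approved before the primary database lock. Death dates are already collected for OS, so deaths within 30 days of the last dose can be checked against the SAE records before then.

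The cost is one sentence in Appendix 3, one statement in the SAP, a flag or footnote, and a few more SAE forms for progression deaths.
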